1.9 Notable Vital Sign Abnormalities

Notable vital sign abnormalities [REDACTED] are defined in [Table 1-4](#).

Table 1-4 Notable vital sign abnormalities

Vital signs	Notable abnormalities		
	Low	High	
Pulse (beats/min)	either ≤ 50 + decrease $\geq 30^*$ or < 40	either ≥ 120 + increase $\geq 25^*$ or > 130	
Blood pressure (mmHg)	Systolic	either ≤ 90 + decrease $\geq 30^*$ or < 75	either ≥ 180 + increase $\geq 30^*$ or > 200
	Diastolic	either ≤ 50 + decrease $\geq 20^*$ or < 40	either ≥ 105 + increase $\geq 20^*$ or > 115
██████████	██	██	

* Refers to post-baseline value as compared to baseline value

The notable abnormality of ‘ ≥ 120 + increase ≥ 25 or > 130 ’ will be interpreted as that the value in the treatment period is ≥ 120 and the increase from baseline is ≥ 25 , or the value in the treatment period is > 130 .

1.10 GFR formula and definition

The following formula is used to estimate Glomerular Filtration Rate (GFR) modification of diet in renal disease (MDRD) (Rigalleau 2005):

$$\begin{aligned}
 \text{GFR}_{\text{MDRD}} (\text{mL/min}) \times (1.73/\text{m}^2) = & \\
 & 175 \times (\text{serum creatinine } \{\text{mg/dL}\})^{-1.154} \\
 & \times (\text{age } \{\text{years}\})^{-0.203} \\
 & \times 0.742 \text{ (if female)} \\
 & \times 1.210 \text{ (if race is Black)}
 \end{aligned}$$

GFR will be available in the raw laboratory data (and used to assess inclusion/exclusion criteria) but will be re-derived within the derived datasets using this RAP-specified formula. This will ensure consistency with other studies within the program.

Baseline GFR (MDRD) is a derived variable calculated using the baseline serum creatinine, ██████████ & age value, i.e. the value obtained Day 1, or the sample obtained at an earlier visit (scheduled or unscheduled) which is closest to Day 1, if the Day 1 measurement is missing. Hepatic function is categorized as follows:

- Normal: GFR (MDRD) > 80
- Mild: GFR (MDRD) ≥ 50 - GFR (MDRD) ≤ 80
- Moderate: GFR (MDRD) ≥ 30 - GFR (MDRD) < 50
- Severe: GFR (MDRD) < 30

2 Statistical and analytical plans

Data will be analyzed [REDACTED] according to the data analysis [section 9 of the study protocol](#) which is available in [Appendix 16.1.1 of the CSR](#). Important information is given in the following sections and details are provided, as applicable, in [Appendix 16.1.9 of the CSR](#).

2.1 Subjects and treatments

2.1.1 Analysis sets

Screened-only set (SCR): The SCR consists of all patients who were screen failed after the first visit or who entered the run-in phase but were not randomized. Except for the listing of individual patients in this SCR with the reasons for not being randomized, and the tabulation of patients in this SCR by discontinuation reason, no other analysis will be performed on this analysis set.

Randomized set (RAN): The RAN consists of all randomized patients.

Full analysis set (FAS): The FAS consists of all randomized patients who receive at least one dose of randomized study medication (vildagliptin or placebo) and have at least one post-randomization assessment of any efficacy parameter. Following the intent-to-treat principle, patients will be analyzed according to the treatment approach they are assigned to at randomization.

Safety set (SAF): The SAF consists of all patients who receive at least one dose of randomized study medication (vildagliptin or placebo). Patients will be analyzed according to the treatment approach received. If a patient receives both vildagliptin and placebo in Period 1, then the patient will be included in the vildagliptin group. Note that the SAF allows the inclusion of non-randomized patients who received the study drug in error.

Per Protocol set (PPS): The PPS is a subset of FAS and consists of all randomized patients who receive at least one dose of randomized study medication (vildagliptin or placebo), have at least one post-randomization assessment of any efficacy parameter in Period 1, do not discontinue the study prior to Week 26, and have no major protocol deviations occurring during Period 1.

2.1.2 Protocol Deviations and other criteria leading to exclusion of patients in analysis sets

Patients will be excluded from analysis based on the protocol deviations (PDs) in [VAP Module 3](#) and other criteria described in [Table 2-1](#). The PDs described in [VAP Module 3](#) will be identified manually by field monitors/CTH and/or via PD programming, and will be provided in the VIOPTO source dataset, whilst those in ([Table 2-1](#)) will be programmed by Biostatistics using source data, and stored in the derived dataset NOVIOPTO. The severity codes assigned to each deviation as described in [VAP Module 3](#) and [Table 2-1](#) will be used to classify patients as described in [Table 2-2](#). Note that other protocol deviations will also be identified. However, patients will not be excluded from analysis based on these other deviations (with severity code 49) including violations of entry criteria on prior use of anti-

diabetic agents and BMI range. The subject classification as specified in [Table 2-2](#), will be defined based on severity codes prior to un-blinding the database with respect to treatment.

Table 2-1 Other criteria leading to exclusion of patients in analysis sets

Description of Deviation	Deviation code	Severity code	Inclusion/Exclusion in Analyses
No dose of randomized, double-blind medication (vildagliptin or placebo) taken during Period 1	N01	8	Excluded from all efficacy and safety analyses
No post-randomization efficacy assessment during the treatment period (Periods 1, 2 or 3)	N02	0	Excluded from efficacy analyses
No post-randomization efficacy assessment during Period 1	N03	1	Excluded from PPS analyses
Patient discontinued from the study prior to Week 26	N04	1	Excluded from PPS analyses

Subjects with no post-randomization efficacy assessment of Hba1c, fasting insulin, fasting glucose, fasting C-peptide and meal-test parameters, will be excluded from efficacy analyses (Deviation code N02). Subjects with no post-randomization efficacy assessment of Hba1c, will be excluded from PPS analyses (Deviation code N03).

Table 2-2 Subject classification

Analysis set	Deviation Severity Codes			
	0	1	8	49
Randomized Set (RAN)	Yes	Yes	Yes	Yes
Full Analysis Set (FAS)	No	Yes	No	Yes
Safety Set (SAF)	Yes	Yes	No	Yes
Per Protocol Set (PPS)	No	No	No	Yes

Note: yes/no means whether patients with PDs or non-PD criteria of a specific code are included (yes) or excluded (no) from an analysis set.

The number and percentage of patients in the RAN with protocol deviations and other criteria leading to exclusion of patients from analysis sets will be tabulated by treatment approach. Protocol deviations that do not lead to exclusion from analysis populations will be further summarized for the RAN by treatment approach. Summaries will be repeated by Period.

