9.1 Analysis sets

The following analysis data sets will be defined for this study.

Screened-only (SCR) set: consists of all patients who were screen failed after the first visit or who entered the run-in phase but were not randomised. Except for the tabulation and listing of individual patients in this SCR set with the reasons for not being randomised, no other analysis will be performed in this analysis set.

Randomised (RAN) set: consists of all randomised patients.

Full-analysis set (FAS): consists of all randomised patients who received at least one dose of study medication and had at least one post-randomization assessment of any efficacy parameter. Following the intent-to-treat principle, subjects will be analysed according to the treatment they were assigned to at randomization.

Safety (SAF) set: consists of all patients who received at least one dose of study medication. Patients will be analysed according to the treatment received.

The Per-protocol set (PPS) is a subset of the FAS. It consists of all randomised patients in the FAS patients who take at least one dose of study medication and have no major protocol deviations affecting the primary endpoint analyses.

The major protocol deviations leading to exclusion from the PPS will be specified prior to unbinding the database with respect to treatment.

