2.1 Subjects and treatments

2.1.1 Analysis sets

Screened-only set (SCR): The SCR consists of all patients who were screen failed after the first visit or who entered the run-in phase but were not randomized. Except for the listing of individual patients in this SCR with the reasons for not being randomized, and the tabulation of patients in this SCR by discontinuation reason, no other analysis will be performed on this analysis set.

Randomized set (RAN): The RAN consists of all randomized patients.

Full analysis set (FAS): The FAS consists of all randomized patients who receive at least one dose of randomized study medication (vildagliptin or placebo) and have at least one post-randomization assessment of any efficacy parameter. Following the intent-to-treat principle, patients will be analyzed according to the treatment approach they are assigned to at randomization.

Safety set (SAF). The SAF consists of all patients who receive at least one dose of randomized study medication (vildagliptin or placebo). Patients will be analyzed according to the treatment approach received. If a patient receives both vildagliptin and placebo in Period 1, then the patient will be included in the vildagliptin group. Note that the SAF allows the inclusion of non-randomized patients who received the study drug in error.

Per Protocol set (PPS): The PPS is a subset of FAS and consists of all randomized patients who receive at least one dose of randomized study medication (vildagliptin or placebo), have at least one post-randomization assessment of any efficacy parameter in Period 1, do not discontinue the study prior to Week 26, and have no major protocol deviations occurring during Period 1.

2.1.2 Protocol Deviations and other criteria leading to exclusion of patients in analysis sets

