2.1.6 Study medication

The study consists of three treatment periods.

In Period 1 patients will be randomized to metformin + vildagliptin 50mg bid, or metformin + placebo. If initial treatment fails to maintain HbA1c < 7.0%, confirmed at two consecutive scheduled study visits (after remapping in [section 1.3.3](#) has been applied), starting from Visit 4 (Week 13), then vildagliptin will be added to metformin in the metformin-only arm in Period 2. The Period 1 end date is defined as the date of the second of the two consecutive scheduled study visits, i.e. the initial treatment failure date. The Period 2 start date is defined as the next day.

In Period 3, insulin is considered based on local guidelines. Both patients and investigators will remain masked to the treatment allocation in Period 1, and the study will compare the two different treatment approaches. The Period 3 start date is defined as the date of insulin initiation. The Period 2 end date is defined as the previous day.

Treatments are referred to as ‘Treatment approach’ throughout this analysis plan to acknowledge that patients are not on the same treatment for the duration of the study. When summaries are detailed for the ‘Treatment Period’, they will include data from Periods 1, 2 and 3, unless specified otherwise.

The duration of exposure to study medication (in months) during the treatment period will be computed for all patients using the algorithm outlined in [Section 1.4](#) and summarized by treatment approach for the RAN both descriptively (i.e., mean, standard deviation, median, minimum and maximum) and by 3 - monthly intervals (0 - < 3 months, 3 - < 6 months, ..., ≥ 60 months).

The study Period 1 duration (in months) will be also similarly summarized for the RAN. The study Period 1 duration is defined as (initial treatment failure date – treatment start date + 1)/30.4375 for patients who entered study Period 2. The study Period 1 duration is the same as overall study duration for patients who did not enter into Period 2.

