2.2.2 Primary efficacy variables

2.2.2.1 Variable definition

The primary efficacy variable is time to confirmed initial treatment failure. The confirmed initial treatment failure is defined as a patient with HbA1c measurements $\geq 7.0\%$ at two consecutive scheduled visits (after remapping in [section 1.3.3](#) has been applied), starting from Visit 4 (Week 13). The time to confirmed initial treatment failure is defined as the time from randomization until the time when the second of the two HbA1c measurement $\geq 7.0\%$ was determined after at least 13 weeks of treatment (Visit 4), i.e. the end of Period 1. The rationale of starting the treatment failures count from Visit 4 is that treatment guidelines consider as treatment failure patients who do not achieve HbA1c $< 7.0\%$ after 3 months of treatment ([ADA-EASD, 2009](#)).

The main study conclusion will be based on the analysis of the primary efficacy variable using the FAS. Analyses based on the PPS will also be performed to assess the robustness of the conclusion.

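### A major deviation at any time in Period 1 removes a patient from the per-protocol set, and Period 1 ends at failure, so per-protocol failure rates can be inflated if deviations accrue over time

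*SAP*

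**What the plan says.** SAP 2.1.1 (same text in V3.0 and Addendum 1) limits the PPS to FAS patients who, among other conditions, "do not discontinue the study prior to Week 26, and have no major protocol deviations occurring during Period 1". SAP 2.1.6 sets the end of Period 1 at the "date of the second of the two consecutive scheduled study visits, i.e. the initial treatment failure date". For everyone else, "The study Period 1 duration is the same as overall study duration for patients who did not enter into Period 2", so up to five years. SAP 2.2.2.1 makes the same link in defining the primary variable: the time at which the second raised HbA1c "was determined after at least 13 weeks of treatment (Visit 4), i.e. the end of Period 1".

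Table 2-2 in SAP 2.1.2 drops patients with an excluding severity code from the PPS altogether. No passage fixes a common exclusion window or censors at the deviation. Protocol 9.1 words the PPS differently (patients must "have no major protocol deviations affecting the primary endpoint analyses") but sets no window either. On its use, SAP 2.2.2.1 bases the main conclusion on the FAS and adds: "Analyses based on the PPS will also be performed to assess the robustness of the conclusion".

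**The concern.** A patient who fails at Week 26 has half a year in which to commit an excluding deviation. A patient who stays controlled has up to five years. If major deviations arise throughout follow-up, long-controlled patients are more likely to be removed. Whether a patient counts in the risk set at Week 26 then depends on what that patient does years later, so Kaplan-Meier and Cox analyses on the PPS condition on the future.

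The PPS is the SAP's named check on robustness, and in a durability trial the share of patients failing by five years matters in its own right. A PPS curve lying above the FAS curve would suggest that adherent patients lose control sooner, although the exclusion rule alone can produce that picture.

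**Working it through.** **Inputs.** From Protocol 9.6 and SAP 2.7: 10% initial failures in each arm; metformin failure rate 7.1% per year; hazard ratio 0.75 afterwards, so 0.75 × 0.071 = 0.05325 per year on the combination; 5 years; 1000 per arm; dropout 4% per year (SAP V3.0) or 11% (protocol). Visits are 13 weeks apart, so the first confirmed failure falls at about Week 26. Assumed, because the documents give no figure: major deviations at a constant rate d of 1-10% per year, independent of failure.

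**The plan's own figure.** The plan gives no figure for deviations; these are its power inputs. A log-rank simulation gives 64.8% power at 11% dropout, against the protocol's 66%, if the failure hazard runs from randomisation and the rates are read as yearly probabilities. Stratifying by baseline HbA1c, with an assumed 20% of patients at 7% or above, also gives 64.8%, and 75.9% at 4% dropout against V3.0's 75%. Starting the hazard at Week 13, unstratified, gives 58-59% at 11% dropout. The plan does not describe its simulation, so this shows only that the inputs are read sensibly.

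**Step 1: chance of exclusion.** With Period 1 of length L, it is 1 − exp(−dL). At d = 3%: 1 − exp(−0.03 × 0.5) = 1.5% for failure at Week 26, and 1 − exp(−0.03 × 5) = 13.9% for control throughout.

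**Step 2: FAS failure at 5 years.** 1 − 0.90·exp(−4.5λ). Metformin: 1 − 0.90·exp(−0.3195) = 34.6%. Combination: 1 − 0.90·exp(−0.2396) = 29.2%.

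**Step 3: PPS failure at 5 years.** Let μ be dropout, a = λ + μ, K = a + d and L = 4.5 years from Week 26. Among patients with no deviation by Week 26:
- a patient failing at that visit is kept; one still controlled is kept with probability R = (a + d·exp(−KL))/K;
- initial failures make up i = 0.10/(0.10 + 0.90R) of the PPS;
- the later cumulative hazard is H = (λ/a)·ln[(a·exp(KL) + d)/K];
- 5-year failure is 1 − (1 − i)·exp(−H).

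Metformin, d = 3%, μ = 4%: a = 0.111, K = 0.141, R = 0.900, i = 0.110, H = 0.338, failure 36.5%.

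| d per year | Metformin, PPS (FAS 34.6%) | Combination, PPS (FAS 29.2%) |
|---|---|---|
| 1% | 35.3% | 29.8% |
| 2% | 35.9% | 30.4% |
| 3% | 36.5% | 31.0% |
| 5% | 37.9% | 32.3% |
| 10% | 41.3% | 35.6% |

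A simulation of 400,000 patients per arm with 13-weekly visits agrees within about 0.2 points. At 11% dropout and d = 3%, metformin is 36.3%.

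**Step 4: hazard ratio (simulated).** The FAS value is about 0.83 rather than 0.75 because the equal initial failures count. It moves from 0.827 to 0.833 at d = 3% and from 0.823 to 0.843 at 10%. With no treatment effect it stays near 1 (0.995 to 0.996 at 3%). At 4% dropout about 614 events are expected (198 initial, 416 later), so the standard error of the log hazard ratio is about 2/√614 = 0.081. The shifts, ln(0.833/0.827) = 0.007 and ln(0.843/0.823) = 0.024, are about 0.1 and 0.3 standard errors. A repeat run at 10% gave 0.827 in the FAS, 0.846 in the PPS and 0.839 with censoring at the deviation, so much of the shift is not due to the exclusion rule.

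**Step 5: when deviation and failure are related.** With 30% of patients deviation-prone, the PPS excess over the FAS falls to about 0.5 points if they fail twice as fast. At three times it reverses slightly (PPS 43.5%, FAS 43.9%), with 42.3% under censoring at the deviation.

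**Step 6: the repair.** At d = 3%, censoring at the first major deviation gives 34.5% and 29.1%, and so does excluding only for deviations up to Week 26. In the simulation both equal the FAS values. Under independence this holds by construction.

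**The case against.** The strongest reply concerns size. SAP 2.1.2 says "Patients will be excluded from analysis based on the protocol deviations (PDs) in" VAP Module 3, which is not among the documents, so neither the excluding deviations nor their frequency is known. Deviations present at entry cause no such bias. Prohibited anti-diabetic treatment requires withdrawal (Protocol 5.5.9), so those cases already sit within the roughly 4% yearly dropout. Rates of 5-10% therefore cannot be called typical. This stands, and it is why the 1-3% cases belong beside them.

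The second reply is that whole-patient exclusion is the usual form of a per-protocol set, that classification is fixed before unblinding, and that deviations are tabulated by arm and Period. These steps guard against selection by arm and show how many patients are affected. They do not remove the dependence on event time.

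Three stronger readings are tempting, and the documents do not support them:
- That the PPS rates are necessarily too high. This needs deviations that accrue over time, and relative to the FAS the direction can reverse (Step 5).
- That the PPS hazard ratio is materially pulled towards 1. The shift is small beside its standard error.
- That the trial's conclusion is compromised. It rests on the FAS, which this rule does not touch.

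**Conclusion.** The point holds in conditional form. The SAP's own definitions make eligibility for the PPS depend on the primary event time, and nothing in either document removes that dependence. The consequence is confined to the supportive analysis, mainly its absolute failure rates and Kaplan-Meier curves: about 0.6 to 2 points in the metformin 5-year rate at 1-3% deviations per year, and about 3 to 7 points at 5-10%, with similar shifts on the combination. These sizes rest on assumed rates, a constant hazard of deviation, and independence of deviation from failure. The condition on discontinuing before Week 26 adds almost nothing, because confirmed failure cannot occur much before then. This is a desirable refinement, not a threat to the primary result.

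**What to change.** For the PPS time-to-event analyses, exclude patients only for deviations present at entry. Keep a patient whose major deviation arises later and censor at its date. An alternative is to exclude only for deviations within a fixed window common to all patients, such as up to Week 26, without later censoring. Report the chosen version beside the present PPS, labelled post hoc if the data are already unblinded; Addendum 1 already labels other additions that way.

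The cost is a change of SAP wording and a dated deviation variable in the derived data. Deviations are already to be summarised by Period, so most of the timing should be available. Censoring assumes that deviation is unrelated to later failure given the covariates. The fixed-window version avoids that assumption but keeps follow-up after the deviation, so it is less strictly per protocol.

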2.1.3 Patient Disposition

The number and percentage of randomized patients (RAN) who completed the study and who discontinued will be tabulated by treatment approach. Discontinuation will be further broken down by reason in the tabulation. Summaries will be repeated by Period, including information about the number of patients continuing into the next Period.

Completion information will be listed for the RAN.

Patients who were screened for the trial and entered the run-in phase but were not randomized (SCR) will be tabulated and listed with reasons for not being randomized. These summaries will include both screen failures and run-in failures (i.e. patients who discontinue within the screening period and patients who discontinue within the run-in period). Note that the patients will be presented together and not separated out into separate groups for screen failures and run-in failures.

2.1.4 Groupings for analysis

The number and percentage of patients in each analysis set will be summarized by treatment approach. The number and percentage of patients included in the meal test, [REDACTED] subsets will also be summarized by treatment approach. Meal test [REDACTED] count data will be presented as part of the efficacy evaluations. [REDACTED]

2.1.5 Background and demographic characteristics

Demographic, background data and key efficacy variables at baseline will be summarized for all randomized patients (RAN) by the treatment approach that patients are assigned to at randomization. Categorical variables gender, race, ethnicity, baseline age group, current smoking status, baseline GFR (MDRD) category, baseline body mass index (BMI) group, and baseline HbA1c group will be summarized by frequency and percentage. The continuous variables baseline age, height, [REDACTED], baseline BMI, duration of T2DM, baseline HbA1c and baseline FPG will be summarized by mean, standard deviation, median, minimum and maximum.

All baseline and background characteristics (except HbA1c, FPG and GFR) will be summarized at study entry (screening visit) or at the randomization visit if screening (Week - 5) measurements are not collected.

Baseline body mass index (BMI) will be calculated (i.e. not taken from the eCRF) from the height and weight measured at screening (Week -5), $BMI = \text{weight} / \text{height}^2$, where weight is in kilograms (kg) and height is in meters (m).

The classification of the baseline HbA1c, BMI, age category and GFR (MDRD) category are based on the following definitions:

- HbA1c category (< 7% and $\geq 7\%$)
- BMI (< 30 kg/m² and ≥ 30 kg/m² at Visit 1)
- Age at Visit 1 by tertiles i.e. <48 years, 48 - < 62 years and ≥ 62 years)
- GFR (MDRD) category (Normal: >80 mL/min, Mild: ≥ 50 mL/min - ≤ 80 mL/min, Moderate: ≥ 30 mL/min - <50 mL/min, Severe: 0 mL/min - <30 mL/min)

Baseline comparability across treatment approaches for all randomized patients (RAN) will be examined in a [Section 16.1 listing](#) using a chi-square test for the categorical variables, and a two-sample t-test for the continuous variables. The p-values are provided for descriptive purposes, and will not to be considered as the formal basis for determining factors to be included in the statistical analysis model.

In addition, all relevant medical history and history of diabetes and complications will be summarized by primary system organ class, preferred term and treatment approach using frequency tables in Post-text tables for all RAN patients.

